The primary analysis will be performed on the ITT population, which consists of all randomized subjects who received at least one dose of study treatment.

The primary endpoint in this study is all-cause mortality through Day 42 and which will be compared between the POS arm and the VOR arm for the ITT population. The primary analysis will be assessed using a non-inferiority margin of 10%. Ninety-five percent Confidence Intervals (CI), adjusted for stratification factors for the difference in success rates (POS minus VOR) will be computed. If upper limit of that CI is less than 10%, then non-inferiority of POS will be declared. If non-inferiority is declared, then superiority of POS over VOR will be assessed and will be declared if the lower limit of the CI is greater than 0.

Secondary endpoints include the global clinical response at Week 6 and Week 12 in the FAS population, all-cause mortality through Day 42 and Day 84 in the FAS population and all-cause mortality through Day 84 in the ITT population. All will be evaluated using a similar methodology as that for the primary analysis.

Other endpoints (i.e., time to death [all causes] in the FAS population; and mortality due to IA at Weeks 6 and 12 in the FAS population) will also be analyzed. Adjudicated global clinical response Weeks 6 and 12 in subjects with possible, probable, or proven IA subjects (ITT population) will also be assessed as a secondary endpoint.

Survival will be assessed using a Kaplan Meier estimates and will be compared between the two arms using the Log-Rank test.

Other analyses: Sparse pharmacokinetic (steady state trough) sampling will be performed on all subjects throughout the treatment period. Data regarding food intake relative to posaconazole tablet administration will be collected and the effect of food on the steady state pharmacokinetics of posaconazole tablet will be evaluated. Plasma concentrations over time in individual subjects including adolescents will be evaluated including an evaluation of plasma concentrations at the time of adverse events. In subjects receiving IV study therapy, at the time of maximum concentration, data regarding ECG parameters will be evaluated. Exploratory analysis may be conducted on pharmacogenomic endpoints and their association with key efficacy and safety parameters at a later date, as data allow.

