^a Subjects will begin IV study drug and then step down/transition to oral study drug. If clinically indicated, some subjects may begin study drug with oral therapy instead of IV therapy.
^b Day 1 refers to the first day of subject taking either IV or Oral therapy. Subjects will only take one formulation, either IV or oral at a time
^c The planned duration of study therapy is 12 weeks (84 days) with a maximum allowable duration of up to 98 days. IV=intravenous; POS=posaconazole; VOR=voriconazole

Diagnostic, attributable mortality, and efficacy data from all subjects will be reviewed by an independent CAC who will be blinded to the assigned treatment arm. The CAC will determine acceptability of the diagnostic criteria of a proven or probable IFI according to modified MSG/EORTC consensus criteria [9]. Subjects who are randomized receive at least one dose of study drug and whose diagnosis of proven or probable IA is confirmed by the CAC will comprise the FAS dataset. (The FAS further requires subjects to have received at least one dose of study drug and have at least one post-randomization observation for the analysis endpoint subsequent to at least one dose of study treatment [and have baseline data for those analyses requiring baseline data]). The CAC will adjudicate the global clinical response to

treatment (as per 2008 EORTC/MSG guidelines) at 6 weeks and at 12 weeks post-randomization. A successful global clinical response will be defined as an FAS-evaluable subject who is judged by the CAC to be alive and have a complete or partial response at the time point of interest. The CAC will also adjudicate IFI-attributable mortality through Day 42 and Day 84 in subjects as data allow.

The primary analysis will be performed on the ITT population. The ITT population consists of all randomized subjects who received at least one dose of study treatment.

The primary endpoint in this study is all-cause mortality through Day 42 between the POS arm and the VOR arm for the ITT population. The primary analysis will be assessed using a non-inferiority margin of 10%. Ninety-five percent Confidence Intervals (CI), adjusted for stratification factors for the difference in success rates (POS minus VOR) will be computed. If upper limit of that CI is less than 10%, then non-inferiority of POS will be declared. If non-inferiority is declared, then superiority of POS over VOR will be assessed and will be declared if the lower limit of the CI is greater than 0.

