8.5.1 Statistical Methods for Efficacy Analyses

All-Cause Mortality

The primary endpoint, corresponding to the primary trial objective, is all-cause mortality through Day 42 in subjects in the ITT population.

The primary analysis is to compare the POS arm to the VOR arm. The difference in mortality rate between arms (POS minus VOR) and the associated 95% confidence interval (CI) on the difference will be calculated using Miettinen and Nurminen's method [13] stratified by risk for mortality/poor outcome (high risk, not high risk). If the upper limit of that CI is less than 10% (the non-inferiority margin), then non-inferiority of POS will be declared. If non-inferiority is declared, it can be further concluded that POS is superior to VOR if the lower limit of the CI exceeds zero. Due to the principle of closed testing, no adjustment for multiplicity is required since non-inferiority can always be concluded whenever the data also supports superiority. Summary statistics and a tabulated treatment comparison will be provided.

Other secondary endpoints include all-cause mortality through Day 42 and Day 84 for the FAS population and will be evaluated using similar methodology as will be used for the primary endpoint in the ITT population.

Mortality will be evaluated through Day 42 and through Day 84 with no time window applied either before or after the target day.

Survival will also be assessed using Kaplan-Meier methodology and compared between the two arms using the Log-Rank test stratified by risk for mortality/poor outcome (high risk, not high risk).

Proportion Of Subjects Achieving Global Clinical Response

A secondary endpoint is global clinical response (partial or complete response defined by the 2008 MSG/EORTC criteria) at 6 weeks post-randomization in the FAS population.

The analysis is to compare the POS arm to the VOR arm. The difference in proportions between arms (POS minus VOR) and the associated 95% confidence interval (CI) on the difference will be calculated using Miettinen and Nurminen's method [13] stratified by risk for mortality/poor outcome (high risk, not high risk). For the analysis, missing or unable to determine responses will be considered as failures.

An assessment between the two treatment arms will be performed on ITT subjects that are excluded from the FAS, looking at potentially key baseline prognostic factors, such as the stratification variable of risk status for mortality/poor outcome.

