8.6 Multiplicity

Efficacy

No multiplicity adjustment is necessary as there is only one primary efficacy hypothesis based on a single efficacy endpoint at a single timepoint. Statistical significance in this setting is equivalent to nominal significance and will be based on a one-sided alpha level of 0.025.

If non-inferiority is declared, it can be further concluded that POS is superior to VOR if the lower limit of the CI exceeds zero. Due to the principle of closed testing, no adjustment for multiplicity is required since non-inferiority can always be concluded whenever the data also supports superiority.

Safety

No multiplicity adjustment will be used for the safety analysis.

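### The superiority rule runs in the wrong direction: on mortality (POS minus VOR), a lower confidence limit above zero means significantly higher POS mortality

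*Combined protocol and SAP*

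**What the plan says.** Section 8.5.1 defines the primary contrast as the difference in Day 42 all-cause mortality, POS minus VOR, with a stratified Miettinen-Nurminen 95% CI. Two decision rules follow:

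- Non-inferiority: "If the upper limit of that CI is less than 10% (the non-inferiority margin), then non-inferiority of POS will be declared".
- Superiority, once non-inferiority is declared: "it can be further concluded that POS is superior to VOR if the lower limit of the CI exceeds zero".

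The same pair of rules, on mortality, stands in the Trial Design part of the Synopsis. Section 8.6 repeats the superiority rule and argues that no multiplicity adjustment is needed because "non-inferiority can always be concluded whenever the data also supports superiority". It sets significance by saying that it "will be based on a one-sided alpha level of 0.025".

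The Efficacy Analysis part of the Synopsis and Section 7.1 keep both rules (superiority "will be declared if the lower limit of the CI is greater than 0") but name another scale: the interval is "adjusted for stratification factors for the difference in success rates (POS minus VOR) will be computed".

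Table 13 mentions a superiority test without giving a direction. Section 8.0 states that there will be no separate SAP, so these are the only statements of the rule in the plan.

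**The concern.** For a mortality difference taken as POS minus VOR, a benefit of POS is a negative number. Superiority should require the whole interval to lie below zero, that is, an upper limit under zero. The plan requires the whole interval to lie above zero, which is evidence of harm.

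Superiority is the only formal claim that follows the primary test. Read literally, the plan could not recognise a real survival advantage. If the direction were reversed after unblinding, the change could be challenged as post hoc. Section 8.0 itself requires a protocol amendment, before any unblinding, for changes to methods tied to the primary hypothesis.

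**Working it through.** **Inputs.** 300 per arm, 23% mortality in both arms, 10% margin, one-sided alpha 0.025 (Synopsis, Sample Size; Section 8.7.2). The interval is Miettinen-Nurminen as in Appendix 7. It is computed here without strata because stratum rates are not given.

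**1. Which scale the plan uses.** Power by the Farrington-Manning formula, for POS minus VOR mortality with the upper limit compared with +10 points:

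- Constrained rates at a difference of 0.10: 0.2874 (POS) and 0.1874 (VOR).
- Null SE = √[(0.2874×0.7126 + 0.1874×0.8126)/300] = 0.03450.
- SE at the true rates = √[2×0.23×0.77/300] = 0.03436.
- Power = Φ[(0.10 − 1.96×0.03450)/0.03436] = Φ(0.942) = 82.7%, as stated in the plan.

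The worked example in Section 8.7.2 (POS 78/300, VOR 69/300) gives a CI of -3.9 to 9.9, again as stated. These counts are deaths, and Section 8.7.1 also compares the upper bound for mortality with 10%. The plan's figures are therefore on the mortality scale.

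**2. Both rules on each possible scale.**

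| Scale of POS minus VOR | Non-inferiority: upper < 10% | Superiority: lower > 0 |
|---|---|---|
| Mortality (Synopsis Trial Design; 8.5.1) | correct | reversed |
| Success (Synopsis Efficacy Analysis; 7.1) | reversed | correct |

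Neither row is correct throughout.

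**3. Observed results with VOR at 69/300.**

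| POS deaths | 95% CI (points) | Rule as written | Upper limit < 0 |
|---|---|---|---|
| 49/300 (16.3%) | -13.0 to -0.3 | non-inferior, not superior | superior |
| 50/300 (16.7%) | -12.7 to 0.05 | non-inferior, not superior | non-inferior only |
| 91/300 (30.3%) | 0.25 to 14.4 | fails non-inferiority | fails non-inferiority |

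91 is the first POS count with a lower limit above zero, and its upper limit is already past 10%. At equal counts (69/300 in each arm) the interval runs from -6.75 to 6.75, a width of 13.5 points. An interval that wide cannot fit between 0 and 10.

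**4. Where the written rule could fire.** Searching all pairs of counts at 300 per arm with VOR mortality under 50%, both conditions are met only if VOR deaths are 23/300 (7.7%) or fewer. Example: POS 38/300 against VOR 23/300 gives 0.16 to 9.98, so significantly higher POS mortality would be called both non-inferior and superior.

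**5. Chance of declaring superiority** (exact binomial enumeration, 300 per arm, superiority tested only after non-inferiority):

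| True POS / VOR mortality | As written | Upper limit < 0 |
|---|---|---|
| 23% / 23% | 0.000 | 2.5% |
| 21% / 23% | 0.000 | 8.5% |
| 15% / 23% | 0.000 | 70.7% |
| 13% / 23% | 0.000 | 89.5% |

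The POS rates of 15% and 13% are illustrative assumptions. A difference of -2 points is the most favourable that Table 17 considers. Under equal mortality the corrected rule has the intended one-sided error of 2.5%.

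**6. The closed-testing sentence.** It needs the superiority condition to imply the non-inferiority condition. With lower limit > 0 it does not: 91/300 against 69/300 meets the first and fails the second. With upper limit < 0 it does, because a limit below zero is also below 10%.

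**The case against.** The best defence is the success-rate label in the Synopsis efficacy text and Section 7.1, where a lower limit above zero would correctly show a POS benefit. It fails because Section 8.5.1 names mortality, the plan's calculations use mortality, and on a success scale the non-inferiority rule would be reversed instead.

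Several points about size do stand:

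- Superiority is tested only after non-inferiority. Taken alone, a lower limit above zero would occur about 78% of the time if true POS mortality were 33% against 23%, but with the non-inferiority step in front the chance is essentially zero. A false claim of superiority needs VOR mortality of about 8% or less, whereas Table 17 covers 18% to 24%. The practical fault is a missed claim of benefit.
- For the same reason the type I error is not inflated. The closed-testing sentence is wrong as reasoning under the written rule, not a source of false positives.
- Under the plan's own scenarios the loss is small: 8.5% power at best with VOR at 23%. The large figures depend on benefits that the plan does not assume.
- For global clinical response, the Synopsis and Section 7.1 carry over a similar method, but Section 8.5.1 and Table 13 give only a difference and a 95% CI. There the risk is ambiguity, not a stated wrong rule.

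**Conclusion.** The concern holds. The superiority rule is reversed in Section 8.5.1, Section 8.6 and the Synopsis Trial Design text. In the Synopsis Efficacy Analysis text and Section 7.1 the scale label conflicts with the endpoint. No section gives the correct direction. At the planned size and a VOR rate near 23%, the written step cannot declare superiority at all, while the corrected step has 70.7% or 89.5% power if true POS mortality is 15% or 13%.

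These figures rest on unstratified intervals, 300 per arm and assumed POS rates. The direction error depends on none of them, and stratification does not change the sign. The non-inferiority test, the margin, the 82.7% power and the sample size are unaffected. The correction must be made because the rule governs a formal claim and no other document in the plan overrides it.

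**What to change.** Amend the protocol before unblinding:

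1. In the Synopsis (Trial Design and Efficacy Analysis), Section 7.1, Section 8.5.1 and Section 8.6, state that, once non-inferiority is declared, superiority of POS is concluded if the upper limit of the 95% CI for the difference in all-cause mortality (POS minus VOR) is below zero.
2. In the Synopsis Efficacy Analysis text and Section 7.1, replace the reference to success rates with all-cause mortality rates.
3. Give the direction in Table 13, and add one sentence saying that for global clinical response a positive difference favours POS.

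The closed-testing sentence can stay, since it becomes true under the corrected rule. The cost is wording only: no extra patients, data or alpha.

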8.5.2 Statistical Methods for Safety Analyses

Safety and tolerability will be assessed by clinical review of all relevant parameters including adverse experiences (AEs), laboratory tests, vital signs, and ECG measurements.

The analysis of safety results will follow a tiered approach ([Table 14](#)). The tiers differ with respect to the analyses that will be performed. Safety parameters or adverse experiences of special interest that are identified *a priori* constitute "Tier 1" safety endpoints that will be subject to inferential testing for statistical significance with p-values and 95% confidence intervals provided for between-group

comparisons. Other safety parameters will be considered Tier 2 or Tier 3. Tier 2 parameters will be assessed via point estimates with 95% confidence intervals provided for between-group comparisons; only point estimates by treatment group are provided for Tier 3 safety parameters.

Adverse experiences (specific terms as well as system organ class terms) and predefined limits of change in laboratory, vital signs, and ECG parameters that are not pre-specified as Tier-1 endpoints prior to database lock will be classified as belonging to "Tier 2" or "Tier 3", based on the number of events observed. Membership in Tier 2 requires that at least 4 subjects in any treatment group exhibit the event; all other adverse experiences and predefined limits of change will belong to Tier 3.

The threshold of at least 4 events was chosen because the 95% confidence interval for the between-group difference in percent incidence will always include zero when treatment groups of equal size each have less than 4 events and thus would add little to the interpretation of potentially meaningful differences. Because many 95% confidence intervals may be provided without adjustment for multiplicity, the confidence intervals should be regarded as a helpful descriptive measure to be used in review, not a formal method for assessing the statistical significance of the between-group differences in adverse experiences and predefined limits of change.

Continuous measures such as changes from baseline in laboratory, vital signs, and ECG parameters that are not pre-specified as Tier-1 endpoints will be considered Tier 3 safety parameters. Summary statistics for baseline, on-treatment, and change from baseline values will be provided by treatment group in table format. In addition, summary statistics for the difference between treatment groups will also be provided, along with nominal p-values for between-group differences. Mean change from baseline over time will be plotted with the corresponding standard errors.

The following four categories are Tier 1 events:

- Hepatic safety: Elevated AST or ALT lab value that is ≥ 3 x the upper limit of normal (ULN) and an elevated total bilirubin lab value that is ≥ 2 x ULN and, at the same time, an alkaline phosphatase lab value that < 2 ULN, as determined by way of protocol-specified laboratory testing or unscheduled laboratory testing;
- CNS and visual safety: Treatment-emergent adverse events (TEAEs) of visual abnormalities (including terms related to visual hallucination, diplopia, nystagmus, photophobia, photopsia, dyschromatopsia, scotoma, hemianopia, optic neuritis, uveitis, optic disc disorder, visual impairment, vision blurred, visual acuity reduced, blindness, optic atrophy, papilledema, and optic neuropathy); confusion, hallucination, altered mental status, cognitive disturbance, dizziness, altered level of consciousness, depressed level of consciousness, asterixis, tremor, seizures, or encephalopathy.

- Dermatologic reactions: TEAEs of rash (including: MedDRA Terms of dermatitis exfoliative, dermatitis bullous, dermatitis allergic, dermatitis allergic, drug eruption, photosensitivity rash, phototoxic skin eruption, rash, rash erythematous, rash macular, rash maculo-papular, rash popular, rash pruritic, rash vesicular, toxic skin eruption, and urticarial);
- Adrenal steroidogenesis: TEAEs indicating adrenal insufficiency or temporally associated TEAEs of hypotension.

CNS and visual AEs are of particular interest in subjects taking VOR. Each of these AEs tends to occur with higher VOR plasma concentration so that they will be analyzed as Tier 1 events. Additionally, severity of these events will be summarized and the time to first occurrence of these events will be analyzed using time-to-event methodology. Association between plasma concentration in both groups may be also explored.

Tier 2 analysis of treatment difference and 95% CI will be provided for the following events based on specific AE categories: (1) at least one adverse experience; (2) drug related adverse experience; (3) serious adverse experience; (4) serious and drug related adverse experience; (5) discontinued study therapy due to an adverse experience. Other AE categories such as SOCs (System Organ Class) or PDLC (Pre-Defined Limit of Change) in which there are more than 4 events in both groups, Tier 2 analysis of treatment difference and 95% CI will also be provided.

Table 14 Analysis Strategy for Safety Parameters

Safety Tier	Safety Endpoint ^a	p-Value	95% CI for Treatment Comparison	Descriptive Statistics
Tier 1	
 •Hepatic Safety •CNS and visual safety •Dermatologic reactions •Adrenal steroidogenesis 	X	X	X
Tier 2	Proportion of subjects: (1) with at least one AE (2) with a drug related AE (3) with a serious AE (4) with serious and drug related AE (5) discontinued study therapy due to an adverse experience Specific AEs, SOCs, or PDLCs (incidence ≥4 of subjects in one of the treatment groups)		X	X
Tier 3	Specific AEs, SOCs or PDLCs (incidence <4 of subjects in all of the treatment groups) Change from baseline in laboratory measurements			X

^a Adverse Experience references refer to both Clinical and Laboratory AEs.

Note: SOC=System Organ Class; PDLC=Pre-Defined Limit of Change; a listing of subjects and their values falling outside the PDLC will also be provided; X = results will be provided; AE = Adverse Experience

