More effective or safer antifungal therapy is sought for patients with IA [26, 28]. POS is a highly active triazole with the potential to have at least similar efficacy to VOR based on animal model data. POS demonstrates a more potent in vitro activity compared to VOR against the most common clinical isolates including *Aspergillus fumigatus* and *A. flavus* [3]. POS may also have some potential advantages in terms of tolerability, drug interactions, and safety. The most common treatment-related adverse events for VOR are visual disturbances, with approximately 21% of subjects experiencing abnormal vision, color changes, and/or photophobia. Similar visual disturbances are observed in $\leq 2\%$ of subjects who have received POS.

VOR is metabolized primarily by the human hepatic cytochrome P450 enzyme CYP2C19. This enzyme exhibits genetic polymorphism, which can cause large differences in the pharmacokinetics of VOR. Individuals are classified as either extensive metabolizers or poor metabolizers of this enzyme, and the distribution of these genotypes varies greatly across different populations. Poor metabolizers have shown, on average, a 4-fold higher VOR exposure compared to the extensive metabolizers. This variability can have significant clinical impact, since VOR exposure can vary greatly between individuals and data suggests that visual

disturbances may be associated with higher VOR plasma concentrations [4]. POS is not affected by genetic polymorphisms since it primarily circulates in plasma as parent compound, and of the circulating metabolites, the majority are formed via UDP glucuronidation.

POS was shown to be effective in an open label, externally controlled salvage therapy trial of 107 patients with proven/probable aspergillosis. The global clinical response rate (complete and partial response) at the end of therapy was 42% in POS treated subjects, compared to 26% in external controls receiving standard therapy [5]. In addition, POS has activity against *Aspergillus spp.* other than *A. fumigatus*, and importantly, against Zygomycetes, which can mimic the clinical presentation of aspergillosis in high risk patients. In this study of refractory IA, there was an exposure response association; subjects in the highest quartile with the highest POS exposure (mean Cavg of 1250 ng/mL) had a higher response (approximately 75%) compared to lower concentration quartiles.

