8.7 Sample Size and Power Calculations

8.7.1 Justification of Non-inferiority Margin for Response Rate

Since both VOR, the current standard of care for IA, and POS are both triazole anti-fungal agents, a non-inferiority design was selected, hypothesizing that POS has at least a similar effect on overall all-cause mortality through Day 42 compared to VOR. In terms of safety, POS may have a better overall profile compared to VOR, notably in terms of hepatic safety, central nervous system and visual side effects. Thus, the intent was to establish POS as an alternative to VOR that was equally efficacious but with improved tolerability.

In terms of assessing non-inferiority, the upper bound of the 95% CI on the difference (POS-VOR) in the all-cause mortality rates will be compared to 10%, the pre-specified non-inferiority margin, as described in Section 8.5.1. A summary of the

statistical power under various assumptions of true clinical mortality rates assuming this margin is presented in Section 8.7.2.

It is noted that the selected margin needs to be relevant in terms of what percentage of the effect VOR above placebo is retained with POS. If the margin for determining the non-inferiority of POS relative to VOR is too large, the possibility exists that POS could be found to be non-inferior to VOR and simultaneously be no better than placebo. Therefore, the size of the non-inferiority margin must be small enough to ensure this does not happen. For example, a NI margin in which more than 50% of the benefit of VOR could be lost would be considered unacceptable. Thus, the rationale for the NI margin of 10% is presented below and based on the preservation of the majority of the effect size (>50%) of VOR compared to placebo under a number of scenarios. Since there are no direct studies of VOR versus placebo in the treatment of IA, the approach consists of linking data from a variety of studies of VOR and the assumed mortality in placebo/untreated patients being treated for acute IA.

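### The single Tier 1 category for CNS and visual events is likely to be decided by visual events, so it says little about CNS safety

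*Combined protocol and SAP*

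**What the plan says.** Section 8.5.2 introduces its list with "The following four categories are Tier 1 events". One of the four is "CNS and visual safety". Its definition opens with "CNS and visual safety: Treatment-emergent adverse events (TEAEs) of visual abnormalities", followed by a bracketed list of visual terms, and continues, in the same bullet, with "confusion, hallucination, altered mental status, cognitive disturbance, dizziness, altered level of consciousness, depressed level of consciousness, asterixis, tremor, seizures, or encephalopathy". The Synopsis and Sections 7.7.2.1 and 8.3.2 give the same four categories, and Table 14 carries the same four entries. Tier 1 endpoints are "subject to inferential testing for statistical significance with p-values and 95% confidence intervals provided for between-group" comparisons. No section defines a visual group or a CNS group on its own.

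Section 8.5.2 adds a severity summary and a time-to-first-occurrence analysis for these events, without saying whether they are split. Section 8.6 applies no multiplicity adjustment to safety.

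On expected rates, Section 5.1 reports for VOR "approximately 21% of subjects experiencing abnormal vision, color changes, and/or photophobia" and at most 2% for similar disturbances on POS. It gives no CNS event rate for either drug. Section 8.7.1 says the POS profile may be better, "notably in terms of hepatic safety, central nervous system and visual side effects".

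**The concern.** The category joins two kinds of event about which the plan knows very different amounts. For visual events it anticipates a gap of about 19 points in favour of POS. For CNS events it gives no rate and only a general expectation. A subject counts once for either kind, so the visual gap carries the pooled proportion whatever the CNS comparison shows.

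At stake is how the Tier 1 result is read. A significant p-value under a label naming both organ systems invites the conclusion that POS is safer on both, and the pooled comparison cannot carry that. Conversely, a CNS imbalance against POS would be diluted by the visual difference and, under some assumptions, would sit inside a pooled result favouring POS. Pooled time to first event has the same weakness.

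**Working it through.** **Calibration.** The plan states no rate or power for this endpoint, so the check starts from its primary power. With 23% mortality in both arms, a 10% margin, one-sided 0.025 and 300 per arm, the unpooled approximation gives SE = √(2 × 0.23 × 0.77/300) = 0.0344, then 0.10/0.0344 − 1.96 = 0.95, or 82.9%. The Farrington-Manning score version gives 82.7%, as the Synopsis states. The score interval code also returns (−3.9, 9.9) for 78/300 versus 69/300, as in Section 8.7.2.

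**Inputs from the plan.** Visual rate 21% VOR and 2% POS (5.1); 300 per arm (8.7.2); two-sided 5% tests (8.5).

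**Assumptions.** VOR CNS rate 5% to 30%; a hypothetical 8-point CNS excess on POS; visual and CNS events independent unless stated. The Tier 1 test method is not named, so a score test consistent with Miettinen-Nurminen is used, unstratified.

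**Formula.** Pooled rate = 1 − (1 − visual)(1 − CNS).

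At a VOR CNS rate of 20%:
- VOR: 1 − 0.79 × 0.80 = 36.8%
- POS, no CNS difference: 1 − 0.98 × 0.80 = 21.6%
- POS, CNS 28%: 1 − 0.98 × 0.72 = 29.4%

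Chance of a significant result:

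| VOR CNS rate | Pooled favours POS, no CNS difference | Pooled favours POS, 8-point CNS excess on POS | CNS-only test detects that excess |
|---|---|---|---|
| 10% | >99.9% | 76% | 81% |
| 20% | 98% | 48% | 63% |
| 30% | 92% | 28% | 55% |

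With the 8-point excess, the pooled test goes significantly against POS in at most 0.05% of these trials.

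**One worked case** (VOR CNS 10%, POS CNS 18%, POS minus VOR):
- Visual alone: −19.0 points (95% CI −24.2 to −14.4)
- CNS alone: +8.0 points (+2.5 to +13.6)
- Pooled: 19.6% versus 28.9%, −9.3 points (−16.2 to −2.5)

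**When both results are significant in opposite directions.** At observed VOR CNS rates of 10%, 20% and 30%, a CNS excess is significant alone from 5.3, 7.0 and 7.7 points. The pooled interval still excludes zero in favour of POS up to 10.4, 7.6 and 5.4 points. The window is wide at 10%, narrow at 20% and gone at 30%. With a true 8-point excess, both occur in the same trial in about 57%, 17% and 2% of trials.

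**Sensitivity.**
- Visual and CNS events never in the same subject: with the 8-point excess, the pooled test favours POS in 78% to 87% of trials (VOR CNS 30% to 10%).
- Full overlap, an extreme bound: at VOR CNS 20% and POS CNS 28%, the pooled rates are 21% versus 28%, against POS.
- VOR visual rate 10%, VOR CNS 20%: 1 − 0.90 × 0.80 = 28.0% versus 29.4%, so no reversal. For VOR CNS rates of 5% to 30%, the pooled test still detects the 8-point excess in only 3% to 8% of trials, against 94% to 55% for CNS alone.

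**The case against.** **The single pooled test is partly inferred.** Section 8.5.2 says each of these events tends to occur at higher VOR concentrations and is therefore Tier 1, and the footnote in 8.3.2 speaks of specific terms within broader categories. Table 14 alone does not show how many tests each entry receives. However, the sentence in 8.5.2 gives the reason for Tier 1 status and defines no separate test, while every list counts CNS and visual as one of four. Term-by-term testing would not produce a CNS group either.

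**Other displays would show an imbalance.** System organ class intervals at Tier 2, severity summaries, intervals for serious events and discontinuations, and eDMC review could all reveal one, and a 95% CI excluding zero is as informative as a two-sided 5% test. This largely stands, with limits. Section 8.5.2 sends only events not pre-specified as Tier 1 to the lower tiers, so intervals for the individual CNS terms are not assured. The Tier 2 threshold is at least 4 subjects in one group in Table 14, but more than 4 events in both groups in the text before it. The plan calls these intervals descriptive.

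**The size rests on inputs the plan does not give.** This stands. The CNS rates and the 8-point excess are assumed. The 21% describes treatment-related events, whereas the endpoint counts all treatment-emergent ones, and 7.7.2.3.1 forbids eliciting specific events. Some overlap is plausible, since visual hallucination is in one list and hallucination in the other.

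**A stronger reading to resist.** A reader might infer that a CNS harm of POS would be hidden, or that one is likely. The documents support neither: they suggest no such harm, Section 8.7.1 expects the opposite, and the safeguards above remain.

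**Conclusion.** The concern holds as one of interpretability: the pooled Tier 1 result is uninformative about CNS safety. On the plan's own visual rates, with 300 per arm and independent events, it favours POS significantly in about 92% to over 99.9% of trials with equal CNS rates. This conclusion needs no assumed harm.

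Reversal is conditional. It needs a CNS excess on POS, a visual gap near that in Section 5.1, limited overlap, and CNS events that are not very common. Poor detection of a CNS excess is less sensitive to the visual gap, since it persists at a VOR visual rate of 10%. Under heavy overlap the pooled comparison can turn against POS. The change is worth making before unblinding, but the point does not touch the primary analysis.

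**What to change.** In Sections 7.7.2.1, 8.3.2, 8.5.2 and Table 14 (and the matching Synopsis text), report two Tier 1 components from the term lists already in 8.5.2: (a) visual events, the bracketed list; and (b) CNS events, confusion through encephalopathy. Give each its own proportions, difference, 95% CI, p-value, severity summary and time to first event, with the pooled figure beside them.

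State before unblinding that visual hallucination belongs to (a) and other hallucination to (b), and that a subject with events in both lists counts once in each.

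The cost is one more unadjusted Tier 1 comparison and one extra set of tables from the same adverse event data. Only the analysis changes; clinical management is not affected.
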